4 STUDY VARIABLES AND COVARIATES

4.1 PRIMARY VARIABLES

The plasma cytisine pharmacokinetic endpoints for this study are as follows:

- C_{max} Maximum observed plasma concentration post dose, directly obtained from the observed concentration versus time profile.
- T_{max} Time of occurrence of C_{max} .
- C_{min} Minimum observed plasma concentration prior to the last daily dose or prior to each scheduled dose change.
- AUC_{0-t} Area under the plasma concentration versus time curve (AUC) from time zero to the last sampling time at which concentrations were at or above the lower limit of quantification (LLOQ), calculated by the linear-up/log-down trapezoidal rule.
- AUC_{0-inf} Total AUC from zero to infinity, calculated as $AUC_{0-inf} = AUC_{0-t} + (C_{last}/\lambda_z)$, where C_{last} is the last measurable plasma concentration and λ_z the apparent terminal elimination rate constant.
- %AUC Residual area or percentage of extrapolated part for the calculation of $AUC_{0-\infty}$, calculated as $100*[1-(AUC_{0-t}/AUC_{0-\infty})]$.
- λ_z Apparent terminal elimination rate constant.
- $t_{1/2}$ Apparent terminal elimination half-life, calculated from $\ln 2/\lambda_z$.

The pharmacodynamic endpoints for this study are as follows:

- Number of cigarettes smoked daily during treatment and at Day 26
- Reduction in number of cigarettes smoked from baseline, daily during study treatment and at Day 26
- Reduction in expired air carbon monoxide (CO) from baseline, during study treatment and at Day 26;
- Number of subjects at Day 26 that did not smoke any cigarettes for the past 24 hrs and had biochemical confirmation of a CO level less than 10ppm on Day 26 (smoking cessation)
- Change from baseline urine cotinine results;
- Change from baseline Tobacco Craving Questionnaire – Short Form (TCQ-SF) scores: total score and component scores for emotionality, expectancy, compulsivity, purposefulness.

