**Figure 1: Marketed Dosing (1.5 mg tablet) and Timing schedule for [REDACTED]**

## 2.3. Recent Cytisine Pharmacokinetic Studies

### 2.3.1. Study CYT-BIO-02-07 in Healthy Subjects

The Phase 1 CYT-BIO-02-07 study enrolled 36 healthy male subjects who received a single oral dose of 1.5 mg cytisine under fasting conditions. Blood sampling and quantitative urine collection for the determination of cytisine in plasma and urine were performed at regular intervals during the treatment period. Physical examinations were performed by the Principal Investigator or designee at the pre-study screening, after admission to the clinical center, and during the evening before drug administration to the post-study examination just prior to discharge from the clinic. Vital signs (blood pressure, heart rate, and temperature) were also performed after admission to the clinical center, during the evening before drug administration, and within 30 min before drug administration (pre-dose), and 2, 4, 12, and 24 h after drug administration during the Treatment Period.

Blood sampling for determination of cytisine concentrations was carried out in the treatment period within 30 min before (pre-dose) and at 5, 10, 20, 30, 40, and 50 min and continued at 1.0; 1.25; 1.50; 1.75; 2.0; 2.25; 2.50; 3.0; 4.0; 5.0; 6.0; 8.0, and 10.0 h after administration of 1.5 mg cytisine (one [REDACTED] tablet). Urine was collected before (baseline) and quantitatively during the intervals 0-3, 3-6, 6-9, 9-12, and 12-24 h after administration of study drug. At the end of each collection interval, individual urine portions were pooled and aliquots were withdrawn from each urine pool. Creatinine concentrations were measured for each urine pool. Plasma and urine levels of cytisine were determined using validated LC-MS/MS analytical methods. Pharmacokinetic parameters of cytisine in plasma that were estimated included  $AUC_{last}$ ,  $AUC_{inf}$ ,  $C_{max}$ ,  $T_{max}$ , and  $T_{1/2}$ .

Results showed that no measurable plasma levels of cytisine were observed 5 min after drug administration. After 10 min, a level exceeding the limit of quantitation (LOQ) was noted in 5 of 36 (14%) subjects; after 20 min, a level exceeding the LOQ was noted in 29 of 36 (81%)

subjects. At 10 h after drug administration, the cytisine plasma levels exceeded LOQ in all subjects. Mean values and other calculated PK parameters are presented in [Table 1](#) (extracted from the Study CYT-BIO-02-07 report).

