## **12.3. Determination of Plasma and Urine Drug Concentrations**

Cytisine concentrations (ng/mL) in plasma and urine will be determined using a validated liquid chromatography tandem mass spectrometry method and will be conducted in accordance with Good Laboratory Practice regulations and guidelines.

The sample analysis will only begin after the last sample of a study subject is collected. All samples from each subject will be analysed in the same analytical batch. In each run, standard and quality control samples will be distributed throughout the batch containing study samples. Samples with concentrations above the ULOQ will be diluted and re-assayed.

Full details, including the lower (LLOQ) and upper (ULOQ) limits of quantification range, will be provided in a Bioanalytical Phase Plan written by [REDACTED]

Plasma and urine samples of withdrawn subjects should also be analysed for drug concentrations and pharmacokinetic parameters (providing withdrawal was not due to withdrawal of consent).

Unacceptable values due to analytical reasons will be handled in accordance with the Bioanalytical Phase Plan.

Details of the methodologies used and the results obtained, including details of re-measured samples, will be given in the Analytical Study Report.

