3.5 SAMPLE SIZE CONSIDERATIONS

A total of approximately 36 subjects will be randomised to the study, with approximately 18 subjects per treatment arm (12 aged 18-65 and 6 aged >65).

No previous pharmacokinetic studies with cytisine have reported the effects of repeated administration, so no estimates of intra-subject variability of C_{max} , C_{min} or AUC are available. No specific hypothesis testing is planned. Post-hoc analyses may be performed for PK or PD effects that may appear significantly different between the dosage groups or age groups. In general, the sample size of 36 should be sufficient to meet the exploratory objectives of the study.

Subjects who withdraw from study at any time after randomisation will not be automatically replaced. Replacement based on the number and reason of withdrawals will be at discretion of the Sponsor, following discussion with the Principal Investigator.

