11.4.3.1 Statistical Analysis of PK Parameters

Dosing Schedule Comparison

The dosing schedule comparison analysis will be performed separately within each of the dose groups.

In order to perform comparisons between schedule changes within each dose group, following logarithmic transformation, C_{max} values (post-last dose on days 3, 12, 16, 20, 24 and 25), and C_{min} values (pre-first dose on days 4, 13, 17, 21 and 25) will be subjected to an analysis of variance (ANOVA) including a fixed effect for study day and a random effect of subject. Point estimates and 90% confidence intervals (CI) will be constructed for the contrasts between consecutive study days using the residual mean square error obtained from the ANOVA. The point and interval estimates will be back-transformed to give estimates of the ratios of the geometric least squares means (LSmean) and corresponding 90% CI. In addition, estimated geometric means will be presented. The analysis will be performed by age group (18-65 yrs, >65 yrs, all ages).

Dose Group Comparison

The dose group comparison will be a between-group analysis.

Following logarithmic transformation, C_{max} , AUC_{0-t} and AUC_{0-inf} values on Day 25 will be subjected to an analysis of variance (ANOVA) including a fixed effect for dose group. Point estimates and 90% confidence intervals (CI) will be constructed for the contrast between the 1.5 mg and 3.0 mg dose groups using the residual mean square error obtained from the ANOVA. The point and interval estimates will be back-transformed to give estimates of the ratios of the geometric least squares means (LSmean) and corresponding 90% CI. In addition, estimated geometric means will be presented. The analysis will be performed by age group (18-65 yrs, >65 yrs, all ages).

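### The Day 25 AUC0-t dose ratio may compare areas over different intervals: depending on the unstated LLOQ, the 3.0/1.5 ratio can read 0 to about 5% too high, and a common-interval AUC0-12 would remove this.

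*SAP*

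**What the plan says.** SAP 4.1 (and Protocol Table 11) measures AUC0-t "from time zero to the last sampling time at which concentrations were at or above the lower limit of quantification". The endpoint of integration is therefore set subject by subject and not at a fixed time. The late Day 25 samples are at 10, 12 and 24 h (Protocol Table 7, SAP 11.4.1).

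In SAP 11.4.3.1, the log-transformed Cmax, "AUC_{0-t} and AUC_{0-inf} values on Day 25" enter an ANOVA with dose group as the only fixed effect. "Point estimates and 90% confidence intervals (CI) will be constructed for the contrast between the 1.5 mg and 3.0 mg dose groups", and the results go to Tables 14.4.2.5 and 14.4.2.6. Protocol 15.7 specifies the same comparison. No AUC over a common interval is planned.

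On the assay limit, Protocol 12.3 says: "Full details, including the lower (LLOQ) and upper (ULOQ) limits of quantification range, will be provided in a Bioanalytical Phase Plan". On inference, SAP 3.5 says: "No specific hypothesis testing is planned". The group size there is "approximately 18 subjects per treatment arm (12 aged 18-65 and 6 aged >65" years.

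**The concern.** If both doses follow the same kinetics, concentrations at 3.0 mg are twice those at 1.5 mg and stay above a fixed LLOQ for longer. Because sampling jumps from 12 h to 24 h, a subject whose 24 h value is below the LLOQ contributes AUC0-12, while one whose value is above it contributes nearly AUC0-24. If the first case is commoner at 1.5 mg, the ANOVA compares a shorter area with a longer one, and the 3.0/1.5 ratio rises for a reason that belongs to the assay and not to the drug.

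Dose groups are the comparison of main interest under SAP 10.6. A natural reading of the ratio is against 2.0, the value under dose proportionality, although the documents set no such benchmark. A systematic upward shift would tilt that reading, and the AUC0-t and AUC0-inf ratios could disagree with no explanation in the table.

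**Working it through.** **Inputs.** Protocol Table 1 (single 1.5 mg dose, last sample at 10 h) gives these arithmetic means: Clast 2.24 ng/mL, λz 0.1758 /h, AUClast 59.80 and AUCinf 73.63 ng·h/mL. The geometric means are 2.10, 0.1726, 57.53 and 70.67. The CVs are 36% (Clast), 19% (λz), 28% (AUClast) and 53% (AUCres). The LLOQ is not given, so 0.01 to 0.88 ng/mL is assumed. The upper end comes from the earlier study: "At 10 h after drug administration, the cytisine plasma levels exceeded LOQ in all subjects", and its lowest 10 h value was 0.88. That bounds the earlier assay, not necessarily this one.

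**Reproducing the protocol's own figure.** The extrapolated share is 100 × (1 − 59.80/73.63) = 18.8%, against 18.33% stated. The small gap is expected between a ratio of means and a mean of ratios. The tail from geometric means is 2.10/0.1726 = 12.17, against 12.19 stated. Log-linear decline after 10 h is consistent with Table 1.

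**Mean profile at 1.5 mg.**
- C12 = 2.24 × exp(−2 × 0.1758) = 1.576 ng/mL
- C24 = 2.24 × exp(−14 × 0.1758) = 0.191 ng/mL, and double that, 0.382, at 3.0 mg
- AUC0-12 = 59.80 + (2.24 − 1.576)/0.1758 = 63.58
- AUC0-24 = 63.58 + (1.576 − 0.191)/0.1758 = 71.45

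The ceiling on this profile has every 1.5 mg subject cut at 12 h and every 3.0 mg subject at 24 h. The ratio is then 2 × 71.45/63.58 = 2.25, or +12%. With the 4.8 h half-life from the 3 mg pilot study it is +15%.

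**Between-subject variation.** 400,000 subjects were simulated with log-normal C10, λz and AUC0-10. The correlations were solved from Table 1: C10 with λz −0.69, AUClast with AUCres 0.47. The 3.0 mg concentrations were set to exactly twice those at 1.5 mg, so the true ratio is 2.00.

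| LLOQ (ng/mL) | 24 h quantifiable, 1.5 mg | 24 h quantifiable, 3.0 mg | AUC0-t ratio | Bias |
|---|---|---|---|---|
| 0.01 | 99.9% | 100% | 2.00 | 0.0% |
| 0.05 | 95% | 99% | 2.005 | +0.2% |
| 0.1 | 79% | 95% | 2.03 | +1.3% |
| 0.2 | 46% | 79% | 2.07 | +3.6% |
| 0.3 | 25% | 62% | 2.09 | +4.7% |
| 0.4 | 14% | 46% | 2.09 | +4.7% |
| 0.5 | 8% | 34% | 2.08 | +4.2% |
| 0.88 | 1% | 11% | 2.05 | +2.4% |

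With carry-over from Day 24 (doses assumed 18 h and 24 h before the Day 25 dose) the peak is +4.5%. A separate simulation of the full Day 25 profile, with absorption, carry-over and 8% assay error, gave 2.02 at LLOQ 0.1, 2.07 at 0.25 and about 2.09 to 2.10 at 0.5.

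**Unaffected measures.** AUC0-inf adds back Clast/λz, so under log-linear decline its ratio is 2.00 whatever the cut. AUC0-12 is 2.00 as long as the 12 h sample is quantifiable. At 1.5 mg that holds in 99.6% of modelled subjects at LLOQ 0.5 and in 90% at 0.88.

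**Scale.** For CV 28%, the log-scale SD is √ln(1 + 0.28²) = 0.275 and the SE at 18 per group is 0.275 × √(2/18) = 0.092. With t = 1.69 on 34 degrees of freedom, the 90% CI factor is exp(±0.155), or 0.86 to 1.17. With 6 per group it is 0.75 to 1.33. The peak bias is ln(1.047)/0.092 = 0.5 SE. At that peak the nominal 90% interval would cover 2.0 about 86% of the time, lying wholly above it in about 12% of trials and wholly below in about 2%.

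**The case against.** The strongest reply is that the bias may not arise. With an assay limit of 0.05 ng/mL or less, nearly everyone is quantifiable at 24 h in both groups. A reader might infer from the definition alone that 1.5 mg subjects will be cut earlier and the ratio will be biased. The documents do not support this, because they defer the LLOQ elsewhere. This stands, and the point is conditional on it.

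Second, the analysis is exploratory: no test or proportionality criterion rests on the ratio, and even the peak bias is well inside the interval. This stands too and limits the weight of the point.

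Third, safeguards exist. AUC0-inf receives the same ratio and interval, %AUC is summarised by dose and age, SAP 11.4.3 reports the time points used for λz, and 24 h concentrations are tabulated. These would help a careful reader detect unequal truncation. They do not correct the AUC0-t ratio, and AUC0-inf is withheld where λz is unreliable.

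A reader might also infer that AUC0-t exaggerates any age difference, because slower eliminators keep a quantifiable 24 h sample. That does not hold in general. With elimination assumed 25% slower in one group and volume unchanged, the modelled between-group ratio was 1.45 for AUC0-inf and 1.40 to 1.49 for AUC0-t across LLOQ 0.01 to 0.88. AUC0-t can therefore fall on either side. AUC0-12 gave 1.31, so it is no replacement for AUC0-inf when age groups are compared.

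**Conclusion.** The point holds in conditional form and is modest. As defined, AUC0-t can cover different intervals at the two doses. Under exact dose proportionality this raises the expected 3.0/1.5 ratio by 0 to about 5%, depending on the LLOQ, with a mean-profile ceiling of +12 to +15% that would need complete separation at 24 h. On average the shift is never downward, since doubling every concentration cannot bring the last quantifiable sample forward.

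The size rests on log-linear decline after 10 h and on carrying fasting single-dose values from healthy men over to fed smokers on Day 25, including those over 65. Slower elimination would raise 24 h levels and move the LLOQ range in which the doses differ. The documents do not show that the bias will occur. They do leave the plan without a safeguard in the AUC0-t ratio itself if it does.

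**What to change.** In SAP 4.1, define Day 25 AUC0-12 for every subject, saying how a 12 h value below the LLOQ is handled. In SAP 11.4.3.1, add it to the dose-group ANOVA and state that the dose ratio is interpreted from AUC0-12 and AUC0-inf. Keep the AUC0-t ratio that Protocol 15.7 specifies, label it supportive, and summarise last quantifiable time by dose group. List the addition in SAP 1.2. There is no need to remove AUC0-t from the comparison.

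The cost is one partial area from samples already scheduled, one more ratio in Tables 14.4.2.5 and 14.4.2.6, and a few SAP sentences. If the Bioanalytical Phase Plan sets an LLOQ of about 0.05 ng/mL or lower, the addition will change little.

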4.2 SECONDARY VARIABLES

The urine cytosine pharmacokinetic endpoints for this study are as follows:

- Ae Amount excreted in urine over time.
- Ae% Percentage of drug excreted in urine.

The safety endpoints for this study are as follows:

- Adverse events (AEs).
- Laboratory safety data (biochemistry, haematology, urinalysis and microscopy).
- Vital signs (supine systolic/diastolic blood pressure, pulse rate and oral temperature).
- 12-lead ECG (heart rate, PR interval, QRS duration, QT interval and QT interval corrected using Fridericia's formula (QTcF interval).
- ECG Holter Monitoring (heart rate, PR interval, QRS duration, QT interval and QTcF interval).

5 DEFINITIONS AND DERIVED VARIABLES

Study drug/IMP: 1.5 mg or 3.0 mg cytosine.

Treatment/dose: 1.5 mg or 3.0 mg cytosine as per commercialised 25-day dosing schedule.

Dose group: 1.5 mg Cytosine, 3.0 mg Cytosine.

Age group: 18-65 yrs, >65 yrs, all ages.

Baseline: In general, baseline is defined by subject and by variable as the last non-missing value (including repeats) before the first dose of study drug. This is normally the pre-dose assessment on Day 1 but if this assessment is missing (or not planned) then the assessment at the Screening/Day -1 visit will be used instead, if available.

For Holter ECG endpoints, a baseline value will be derived for each subject and ECG parameter (heart rate, PR interval, QRS duration, QT interval and QTcF interval) by calculating the mean of all individual results recorded prior to the administration of study drug on Day 1 (i.e., at the -30 minute and -15 minute time points).

Study Day: Study day is the number of days since start of treatment where the date of first dose is counted as Day 1.

Bleed Time Deviation: Actual time of blood sample – theoretical time of blood sample.

Protocol Deviation: a deviation related to study inclusion or exclusion criteria, conduct of the trial, subject management or subject assessment. This refers to any change, divergence, or departure from the study design or procedures defined in the protocol. Deviations recorded by the Project Manager or detected by Data Management or by statistical programming checks will be identified and discussed at the Data Review Meeting (DRM) before Database Lock (DBL). All protocol deviations within the study database will be classified as either 'Major' or 'Minor' prior to DBL, details of which will be included within the Protocol Deviations listing.

Duration of Exposure: (Date of last dose of cytisine – date of first dose of cytisine) + 1.

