#### On Day 25:

1. All subjects to have breakfast 30 minutes prior to final dose.
2. Attach ECG Holter monitor, checking to ensure recording has started. NOTE: Holter monitors to remain attached to subjects approximately 24 hours, discontinued on Day 26.
3. Record Vital signs (supine blood pressure, pulse rate and oral temperature).
4. Obtain pre-dose PK blood sample (Section 12.1).
5. Begin urine collection for PK as outlined in (Section 12.2).
6. Subject to take final Day 25 dose of cytisine (documenting time of dose in diary) after breakfast and begin extensive PK blood and urine sampling as outlined in (Section 12.1) throughout day and up through 24 hours post.
7. Obtain 12-lead ECG (triplicate) if clinically indicated.
8. Record any adverse events and update concomitant medications.
9. The number of cigarettes smoked will be recorded in the CRF.
10. All subjects will remain in the clinic overnight.

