### **15.9.1. Holter ECGs**

The following ECG parameters will be extracted in triplicate from Holter recordings on Day 1 and Day 25 at 30 and 15 minutes prior to the first dose and 0.5 h, 1 h, 2 h, 3 h, 4 h, 6 h, 8 h, 12 h and 24 h post dose:

- Heart Rate (HR)
- PR intervals
- QRS
- QT
- QTcF

If a large change in heart rate is observed during the study, the individual QT correction method (QTcI) will be used as the primary QT correction method.

The extracted ECG parameters will be listed with any out of normal range values flagged (“H” -high or “L” -low). The ECG results will be assessed as either “normal” or “abnormal”. Any comments on abnormal results will also be provided. Descriptive statistics of absolute and change from baseline values at each time point will be tabulated by dose group and age group (18-65, >65 and overall).

In addition, frequencies of QTcF data will be calculated according to the following categories:

For absolute values:

- $QTcF \leq 450$  mSec
- $450 < QTcF \leq 480$  mSec
- $480 < QTcF \leq 500$  mSec
- $QTcF > 500$  mSec.

For change from baseline:

- QTcF increase  $\leq 30$  mSec
- $30 < QTcF$  increase  $\leq 60$  mSec
- QTcF increase  $> 60$  mSec.

Abnormalities in ECGs will be classified in terms of clinical significance. Clinically significant abnormalities will be reported as AEs. The number and percentage of subjects developing new ECG abnormalities will be summarised. The presence of outliers will be explored for heart rate, PR, QRS, QT and QTcF. Details of this analysis will be described in the Statistical Analysis Plan (SAP).

In order to explore the effects of cytisine on QTc prolongation, plasma concentrations will be plotted against change from baseline QTcF values.

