1.2 CHANGES FROM PROTOCOL

- Change from baseline Tobacco Craving Questionnaire – Short Form scores will be included as a pharmacodynamic endpoint.
- The protocol identified reduction in smoking as a pharmacodynamic endpoint but did not refer to smoking cessation as an endpoint. Smoking cessation has been included in this SAP as a pharmacodynamic endpoint.
- Summaries of smoking cessation will be presented.
- Individual QT corrections (QTcI) will not be performed because it was not feasible for this study as a substantial amount of pre-treatment data across a large range of heart rates was required.
- Inclusion of an ECG analysis set and ECG-PK analysis set.
- The summary of Holter ECG QTcF categories will not include the categories QTcF \leq 450 mSec and QTcF increase \leq 30 mSec.
- Summaries of prior and concomitant medications will be included.
- Smoking history at baseline will be summarised.

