11.6.4.2 Holter Monitoring

The ECG extraction time points will be from extraction windows which precede the PK blood draws. ECG parameters (heart rate, PR interval, QRS duration, QT interval and QTcF interval) will be extracted in triplicate from Holter recordings on Day 1 and Day 25 at 30 and 15 minutes prior to the first dose and at 0.5h, 1h, 2h, 3h, 4h, 6h, 8h, 12h and 24h post dose.

The extracted ECG parameters will be listed with any out of normal range values (see Appendix 1) flagged (flag 'H' or 'L' appended to relevant result). The ECG results will also be assessed as either 'normal' or 'abnormal' with comments on abnormal results also presented.

The mean of the triplicate recordings at each time point will be calculated for use in the summary tables and plots. Any ECG traces that are determined to contain a technical error will not be included in the calculation of the mean values. At each time point, the mean value will be derived from all ECGs (generally three) that are free of technical errors. Descriptive statistics (N, n, mean, SD, minimum, median and maximum) of absolute and change from baseline (see definition, Section 5) values on Day 1 and Day 25 at each time point up to 24h, will be tabulated for each dose group and age group. The change from baseline ECG results will also be plotted over time by dose group and age group.

In addition, frequencies of QTcF data will be calculated according to the following categories:

For absolute values:

- QTcF > 450 mSec
- QTcF > 480 mSec
- QTcF > 500 mSec

For change from baseline:

- QTcF increase > 30 mSec
- QTcF increase > 60 mSec.

The presence of outliers will be explored for heart rate, PR interval, QRS duration, QT interval and QTcF interval). The outlier analysis will use the time-averaged baseline (see definition, Section 5) and compare that baseline value to each of the individual on-treatment ECG time point values. Outliers are defined as follows for this analysis:

- Heart rate: A value for a subject will be considered to be an outlier at a pre-defined post dose time point if the heart rate measurement at that time point is <50 bpm and the measure is at least a 25% decrease from the subject's baseline mean heart rate (i.e., a bradycardic event) or if the heart rate measurement at the pre-defined post dose time point is >100 bpm and the measure is at least a 25% increase from the baseline mean heart rate (i.e., a tachycardic event).

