11.7 PK/PD

In order to explore the effects of cytisine on QTc prolongation, individual cytisine concentrations in plasma and individual (mean of triplicate recordings) absolute and change from baseline Holter QTcF values will be presented together in a listing. A scatter plot will be produced with the individual change from baseline Holter QTcF values at the extraction time points 0.5h, 1h, 2h, 3h, 4h, 6h, 8h, 12h and 24h plotted against the corresponding cytisine concentrations. Both dose groups will be presented on the same plot along with their correlation coefficients with plots for each age group (18-65, >65, all ages) presented separately.

Holter ECG versus plasma concentration data will be listed for the Safety Set and plotted for subjects in the ECG-PK Set.

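### Day 25 Holter change is taken only from the Day 1 pre-dose baseline, so it cannot separate the acute dose effect from a sustained non-drug shift; add a supplementary change from the Day 25 pre-dose ECGs already extracted

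*SAP*

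**What the plan says.** **Baseline.** SAP section 5 obtains the Holter baseline for heart rate, PR, QRS, QT and QTcF by "calculating the mean of all individual results recorded prior to the administration of study drug on Day 1", that is, from the -30 and -15 minute extractions.

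**Use on Day 25.** SAP 11.6.4.2 tabulates "change from baseline (see definition, Section 5) values on Day 1 and Day 25 at each time point up to 24h". The outlier analysis refers to the same definition. The QTcF increase categories (>30 and >60 ms) also need a baseline, and no other Holter baseline is defined. In SAP 11.7, "A scatter plot will be produced with the individual change from baseline Holter QTcF values" against the corresponding concentrations, with both dose groups on one plot and correlation coefficients shown.

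**Day 25 pre-dose data.** The same SAP section has ECG parameters "extracted in triplicate from Holter recordings on Day 1 and Day 25 at 30 and 15 minutes prior to the first dose"; Protocol 15.9.1 likewise lists "Day 25 at 30 and 15 minutes prior to the first dose". No change from these values is planned.

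**Conditions on the two days.** Protocol 11.2.3 gives the first Day 1 dose after a fast of at least 10 hours, with breakfast after the dose. For Day 25, Protocol 11.2.11 states: "All subjects to have breakfast 30 minutes prior to final dose". Subjects enter smoking at least 10 cigarettes a day (Protocol 6.1.1), and reduced smoking is part of a primary objective (Protocol 4.1).

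**Rate correction.** Protocol 15.9.1 held an individual correction in reserve for a large heart-rate change. SAP 1.2 says "Individual QT corrections (QTcI) will not be performed", on grounds of feasibility, so Fridericia's formula alone remains.

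**The concern.** Secondary objective 3 asks about QT/QTc effects and cardiac safety on Day 1 and Day 25. A change on Day 25 from a baseline 24 days earlier has three sources: the dose just taken, drug carried over from earlier doses, and anything else that has changed since Day 1. In a trial meant to reduce smoking, the third source is expected. With no placebo arm and no drug-free Holter day late in the study, the planned outputs do not isolate it.

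A shift opposite in sign to a drug effect would mask that effect; one of the same sign would mimic or inflate it. The concentration-QTcF plot is the most exposed output, because high concentrations arise on Day 1 and low ones mostly on Day 25. Any systematic difference between days is then partly a difference between concentrations. The scheduled 12-lead ECGs do not close the gap: they use a Day -1 baseline and are not scheduled on Day 25 (SAP 11.6.4.1).

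**Working it through.** The plan states no figure for this point, so there is none to reproduce.

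**1. What each reference measures.** Let B be the Day 1 pre-dose mean, P the Day 25 pre-dose mean and Y(t) a Day 25 post-dose value. Let A(t) be the acute effect of the Day 25 dose, R(t) the effect carried from earlier doses, R0 its value before the Day 25 dose, and s a sustained non-drug shift.

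- Planned: Y(t) - B = A(t) + R(t) + s
- Pre-dose shift: P - B = R0 + s
- Against Day 25 pre-dose: Y(t) - P = A(t) + R(t) - R0

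The shift s cancels only in the third line, and part of the cumulative drug effect cancels with it.

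**2. Heart rate and QTcF.** A non-drug heart-rate shift enters the heart-rate change one for one. For QTcF it matters if the true QT-RR exponent b differs from 1/3. Assuming 75 bpm, a QTc of 400 ms and b from 0.25 to 0.40 (none of these is in the documents), QTcF = 400 x RR^(b - 1/3), with RR = 60/HR:

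| Fall in heart rate | Spurious QTcF change |
|---|---|
| 5 bpm | -2.3 to +1.8 ms |
| 10 bpm | -4.8 to +3.8 ms |
| 15 bpm | -7.5 to +5.9 ms |

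It is zero at b = 1/3. Any direct effect of smoking on QTc would be additional, and the documents do not quantify it.

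**3. Time-matched pairs.** ECGs are extracted at 0.5, 1, 2, 3, 4, 6, 8, 12 and 24 h. Day 1 plasma (SAP 11.4.1) is drawn to 2 h after the first dose and again around the last dose. With six doses 2 h apart, the last is at 10 h, so its 2 h sample falls at 12 h. Day 1 therefore gives 4 pairs (0.5, 1, 2 and 12 h). Day 25 has plasma at all 9 extraction times. Total: 13 pairs per subject.

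**4. Concentrations.** One-compartment superposition over all 100 doses, each contributing in proportion to ka/(ka - ke) x (exp(-ke t) - exp(-ka t)). Inputs: ka = 2.81/h, half-life 4.09 h with range 2.74 to 6.36 h (Protocol Table 1), and 4.8 h from the 3 mg pilot study (Protocol 2.3.2). Here r0 is the correlation, over the 13 pairs, of concentration with a Day 25 indicator. It equals the correlation produced by a pure Day 25 shift with no drug effect and no noise; its sign is opposite to that of the shift.

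| Half-life (h) | Day 1 12 h value / highest Day 25 pair | r0 in magnitude |
|---|---|---|
| 2.74 | 2.0 | 0.62 |
| 4.09 | 2.6 | 0.56 |
| 4.8 | 2.7 | 0.52 |
| 6.36 | 2.9 | 0.45 |

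**5. Adding noise.** The indicator has variance (4/13) x (9/13) = 0.213, SD 0.4615. For shift s and residual SD σ:

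|r| = r0 x 0.4615s / sqrt(0.213s² + σ²)

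The values s = 2 to 5 ms and σ = 5 to 10 ms are assumed.

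- Largest (2.74 h, s = 5, σ = 5): 0.62 x 2.31 / sqrt(5.3 + 25) = 0.26
- Smallest (6.36 h, s = 2, σ = 10): 0.45 x 0.92 / sqrt(0.85 + 100) = 0.04

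**6. Residual drug in the Day 25 reference.** Two Day 24 doses 6 h apart, the first at the usual morning time, put the last 24 - 6 = 18 h before the Day 25 dose. The protocol calls it an evening dose, so 12 h is also shown.

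| Half-life (h) | Pre-dose / Day 25 peak, 18 h gap | 12 h gap |
|---|---|---|
| 2.74 | 2% | not calculated |
| 4.09 | 8% | 19% |
| 4.8 | 12% | 25% |
| 6.36 | 22% | 36% |

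**The case against.** A drug-free, pre-treatment baseline is a sound choice for the cumulative on-treatment effect, and a Day 25 reference would remove part of that effect. The study is exploratory with no hypothesis test planned, the absolute QTcF categories (>450, >480, >500 ms) need no baseline, and Day 1 Holter results are untouched. Individual Day 25 pre-dose values will be listed, and SAP 11.6.4.2 can be read as tabulating them. All of this stands. It is why the Day 1 baseline should remain the main analysis.

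Some stronger readings are tempting but not supported:

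- **A bias of several milliseconds at peak exposure.** Multiplying a fitted slope by the modelled Day 3 peak gives -1.1 to -1.5 ms per ms of shift. That omits the intercept; the fitted line at that point moves by only -0.15 to -0.38 ms per ms. The SAP plans no regression line, and no Holter is recorded on Day 3.
- **Meal state as an equal confounder.** Breakfast on Day 1 follows the first dose, so most Day 1 post-dose ECGs are also fed against a fasted baseline. Meals are a minor factor here.
- **Acute smoking on one day only.** The rule of no cigarette within 2 h of dosing (Protocol 7.2.1) covers both days. The exposure of interest is the sustained change in smoking.
- **A missing -30 minute extraction because breakfast is listed before Holter attachment.** The Day 25 list is a set of tasks, not a timeline: it starts urine collection after breakfast, although Protocol 12.2 takes the pre-dose urine on waking. Both documents already require the -30 minute extraction.

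Pooling of the two days in one correlation is also an inference. SAP 11.7 does not say, and the output shells are redacted.

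**Conclusion.** The point holds as a gap in the analysis, not as an error in the Day 1 baseline. The planned Day 25 changes in heart rate, QT and QTcF cannot be divided into acute dose effect and sustained non-drug shift, although the data for that contrast are collected.

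The size is unknown, because the documents give neither the shift nor a residual SD for QTcF. Heart rate is affected directly; for QTcF, the part arising from rate correction can take either sign or be zero. If the days are pooled, the induced correlation is modest once noise is allowed for (about 0.04 to 0.26 under the stated assumptions). The noise-free 0.45 to 0.62 is a ceiling for the half-lives considered, not a forecast.

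These figures rest on a one-compartment model, exact dosing intervals, one typical subject and a shift that is constant through Day 25. Dropping the individual QT correction leaves Fridericia's formula alone, but the SAP explains that decision and the remedy below does not depend on reversing it.

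**What to change.** Keep the Day 1 pre-dose mean as the main Holter baseline. Then:

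1. **SAP 5 and 11.6.4.2:** define a supplementary Day 25 reference from the Day 25 pre-dose Holter values. Present Day 25 change from it beside the Day 1-baseline version. Show the -30 and -15 minute values separately as well as their mean, because the first coincides with breakfast.
2. **SAP 11.6.4.2:** report the Day 25 pre-dose minus Day 1 pre-dose shift in heart rate and QTcF by smoking cessation status. This is descriptive: the groups are small, cessation status is determined after treatment starts, and the shift includes any residual drug effect.
3. **SAP 11.7:** mark Day 1 and Day 25 points separately in the concentration-QTcF plot, give correlations by day, and add the supplementary Day 25 version.

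The cost is SAP wording and one extra set of outputs from ECGs already extracted; the order of Day 25 procedures need not change. The drawback is that the Day 25 reference holds residual drug, about 2 to 22% of the Day 25 peak with an 18 h gap and up to about 36% with 12 h. It therefore tends to understate the full drug effect, which is why both versions should be shown.
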